- B. Pre-ejection period: Pre-ejection period (i.e., PEP, or, the time period during which the left ventricle of the heart contracts while the aortic and mitral valves are still closed) is an established measure of *sympathetic* autonomic activity that can be measured non-invasively using impedance cardiography^{42,44}. Using the same Biopac MP150 monitoring system used to assess heart rate variability (see above), cardiac impedance measurements will be obtained at baseline and at 12 weeks for visits at the [name] site only. According to established protocols⁴⁶, a standard tetrapolar electrode system will be attached to each participant while in the seated position (two inner electrodes placed at the xiphisternal joint and the base of the neck, outer electrodes place 3 cm distally to the inner electrodes). Impedance cardiogram recordings will be obtained by the Biopac monitor at the same time that heart rate variability recordings. Prior to measurement, women will be queried about any history of heart murmurs suggesting heart valve abnormalities that could influence pre-ejection period interpretation. Cardiac PEP will be determined by calculating the time between ventricular depolarization (assessed by ECG output) and the B point of the dZ/dt wave (measured by impedance cardiography). Standard Mindware software will be used to generate the dZ/dt waveform by averaging minute-to-minute ECG and impedance data for each subject.

D.5.3. Anxiety and perceived stress (assessed at baseline, 6 week, 12 weeks, and 24-week mail-in)

Validated self-administered questionnaires will be used to gather additional information about somatic and cognitive anxiety, depression, and perceived stress.

- A. Somatic anxiety: Somatic anxiety (i.e., the affective component of anxiety believed to be related to autonomic physiological arousal response) will be measured using the trait component of the Spielberger State Trait Anxiety Inventory (STAI), a 20-item self-administered measure validated in both clinical and psychiatric populations, including patients with bladder symptoms.^{47,48} Scores range from 20 to 80, with higher scores indicating greater somatic anxiety.

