- B. Cognitive anxiety: Cognitive anxiety (i.e., the mental component of anxiety associated with fear of failure) will be measured by the Hospital Anxiety and Depression Scale (HADS), a validated self-administered questionnaire that includes a 7-item Anxiety Subscale⁴⁹ shown to be sensitive to change in incontinence trials.⁵⁰ Scores range from 0 to 21, with higher scores indicating greater anxiety.
- C. Depressive symptoms: Depressive symptoms will be assessed by the Center for Epidemiologic Studies Depression Scale, a 20-item measure that has been widely used in clinical trials, including trials of bladder interventions, and is sensitive to change.⁵¹ Total scores range from 0 to 60, with higher scores indicating greater likelihood of depression.
- D. Perceived stress: Perceived stress will be assessed using the Cohen Perceived Stress Scale (PSS), a 10-item self-administered questionnaire assessing subjective feelings and thoughts related to perceived stress in the past month, validated in a probability sample of the United States.⁵² Scores range from 0 to 40, with higher scores indicating greater perceived stress.

D.5.4 Respiratory parameters

Respiratory parameters will be measured daily throughout the study by participants' RESPeRATE devices. The RESPeRATE device automatically collects data on respiratory parameters such as average and range of respiratory rate during each practice session. Additionally, the active RESPeRATE device collects data on effectiveness of slow-paced respiration (minutes of breathing in each session in which the respiratory rate was under 10 BPM) and device 'followness' (percent time that breathing was synchronized with the guiding tones). Data are downloaded directly from the device, providing an objective and blinded measurement of respiratory status during sessions. Decrease in respiratory rate with preserved 'followness' indicates that a participant has successfully paced her respiration at a lower rate without holding her breath, and is associated with improvement in blood pressure in prior research⁵³.

D.5.5 Actigraphy (assessed at baseline and at 12 weeks at the [name] site only)

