Sample size is calculated based on parameter estimates derived from prior trials conducted by the investigators, such as BRIDGES and PRIDE:^{64,65} a) mean baseline frequency of urgency- associated voiding or incontinence episodes of 12; b) mean reduction in frequency in controls of 30%; c) standard deviation (SD) of change in urgency-associated voiding or incontinence frequency of 5.8 and d) correlation between baseline and follow-up values of 0.59. We assume that a clinically significant effect in the primary outcome would be a net reduction in the active group of more than 20% than that of controls. Under these assumptions, a sample size of 160 (80 per group) would provide 80% power in 2-sided tests with type-I error of 5% to detect between-group differences of >20% in the active vs. control arm. This accounts for reduction in the residual variance achieved by adjustment for baseline frequency, as well as loss to follow-up of 15%. In comparisons of changes in secondary outcomes (other OAB symptoms, impact scores, anxiety, and autonomic parameters), the sample will provide 80% power in 2-sided tests with type-I error of 5% to detect differences of 0.5 SDs, depending on within-subject correlation of outcomes, assumed to fall in the range of 0.4 to 0.8.

D.10.3 Drop-out rates

Given that the proposed trial is of short duration, dropout levels are expected to be low (i.e., less than 15%). The assumption of non-informative dropout will be examined by comparing baseline and early post-randomization characteristics of dropouts and non-dropouts. If dropout is differential between groups, analyses will be adjusted for maldistributed variables. In a sensitivity analysis, we will also use multiple imputation of missing outcomes, in conjunction with standard methods for calculating summary estimates, confidence intervals, and p-values.⁶⁶

D.10.4 Dose effects

In the event that treatment appears effective in improving OAB symptoms over 12 weeks, we will use a closed test procedure to assess for a dose response in duration of treatment without inflating type-I error:⁶⁷ specifically, if we detect a statistically significant benefit over 12 weeks at an alpha of 0.05, we will then assess change from baseline to 6 weeks, and from 6 to 12 weeks, also at alpha of 0.05. In exploratory

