analyses, we will also assess for a dose response in cumulative time of effective breathing practice, by examining the relationships between total minutes of effective practice and OAB outcomes at 12 weeks, controlling for baseline levels of outcomes. These analyses will allow for assessment of the extent to which differences in adherence and treatment exposure influence treatment benefits on OAB.

D.10.5 Subgroup analyses

Differences between treatment groups will be analyzed in pre-defined subgroups based on clinicopathologic factors in multivariate analysis. For example, we will explore whether high baseline levels of autonomic imbalance or anxiety, past use of medications or other OAB treatments, or baseline use of psychoactive medications influence treatment-associated changes in outcomes. Subgroup-specific effect estimates will be considered only if the interaction with the subgroup is significant at $p < 0.05$.

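### Baseline anxiety and autonomic imbalance enter the subgroup analysis as an undefined high category; a continuous-score interaction needs no cut-point and is more powerful if modification is roughly linear

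*Combined protocol and SAP*

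**What the plan says.** Section D.10.5 (Subgroup analyses) plans to compare the arms within subgroups that it describes as defined in advance. As examples it says "we will explore whether high baseline levels of autonomic imbalance or anxiety, past use of medications or other OAB treatments", and baseline psychoactive medication, influence the treatment effect. It then sets a gate: "Subgroup-specific effect estimates will be considered only if the interaction with the subgroup is significant at $p < 0.05".

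The section does not say which anxiety or autonomic measure defines a high level, or where the line falls. It plans no interaction between treatment and a continuous score.

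The candidate measures are graded scores. For the STAI, D.5.3 says "Scores range from 20 to 80, with higher scores indicating greater somatic anxiety"; for HADS anxiety, "Scores range from 0 to 21, with higher scores indicating greater anxiety". Section D.5.2 derives heart rate variability and pre-ejection period as continuous quantities, measured at one site only. Elsewhere the plan keeps such quantities whole: D.10.1 analyzes anxiety and autonomic outcomes by ANCOVA adjusted for their baseline values, and D.10.4 relates total minutes of effective practice to outcome.

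**The concern.** The trial's background links overactive bladder to anxiety and autonomic dysfunction. Whether benefit varies with their baseline level is therefore the modifier question closest to the rationale. Reducing a graded score to high versus not high discards the differences within each group. If the treatment effect changes steadily along the score, the interaction test loses power, and a true interaction is more often reported as absent.

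The second issue needs no power assumption. With several anxiety scores, several autonomic parameters and no stated cut, a choice made after the data are seen could decide whether the interaction passes the gate.

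Past treatment and psychoactive medication use are categorical by nature and are not affected.

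**Working it through.** **Inputs from D.10.2.** Sample size and power: "a sample size of 160 (80 per group) would provide 80% power in 2-sided tests with type-I error of 5"%. Baseline: "mean baseline frequency of urgency- associated voiding or incontinence episodes of 12". Effect: "net reduction in the active group of more than 20% than that of controls", taken as 0.20 × 12 = 2.4 episodes. Spread: "standard deviation (SD) of change in urgency-associated voiding or incontinence frequency of 5.8". Correlation of baseline with follow-up 0.59; loss to follow-up 15%.

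**Assumptions not in the documents.** A normally distributed modifier; linear modification of *b* episodes per SD of the score; the cut-point (median or top quartile); the values of *b*.

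**1. The plan's own figure (main effect).**
- SD at one time point: 5.8/√(2 × (1 − 0.59)) = 6.41.
- ANCOVA residual SD: 6.41 × √(1 − 0.59²) = 5.17.
- Completers: 160 × 0.85 = 136, or 68 per arm.
- SE of the difference: 5.17 × √(2/68) = 0.887.
- Power at exactly 2.4: Φ(2.4/0.887 − 1.96) = 77.2%.
- Difference detectable with 80% power: 2.485 episodes, or 20.7% of 12.

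This fits the plan's loose wording of more than 20%, although it is not 80% at exactly 20%. If 5.8 were the SD at a single time point, the residual SD would be 4.68 and the power 84.8%. The documents give no power for any interaction, so there is no interaction figure to reproduce.

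**2. Continuous interaction.** With 1:1 allocation, the SE of the interaction per SD of the score is 2 × 5.17/√136 = 0.887. The noncentrality is *b*/0.887.

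**3. Effect of cutting.** If the top fraction *p* is called high, the noncentrality is multiplied by φ(z₁₋ₚ)/√(p(1 − p)).
- Median: 0.399/0.5 = 0.798. Its square is 2/π = 0.64, the share of information kept.
- Top quartile: 0.318/0.433 = 0.734. Its square is 0.54.

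**4. Power at two-sided 5%, 136 completers, residual SD 5.17.**

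| *b* (episodes per SD) | Noncentrality, full score | Full score | Median split | Top quartile |
|---|---|---|---|---|
| 0.6 | 0.68 | 10.4% | 8.4% | 7.9% |
| 1.0 | 1.13 | 20.4% | 14.7% | 13.2% |
| 1.2 | 1.35 | 27.2% | 19.0% | 16.8% |
| 1.74 | 1.96 | 50% | 35% | 30% |
| 2.4 | 2.71 | 77.2% | 57.9% | 51.0% |

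Simulation with 4,000 trials per setting gave 26.6% against 18.9% at 1.2, and 75.1% against 56.0% at 2.4, for full score against median split.

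**5. Sensitivity.**
- *Residual SD 4.68:* the median-split loss is 9.9 points at 1.2 and 18.4 at 2.4.
- *Autonomic modifiers:* one site only, number not stated. With an assumed 100 completers the median-split loss is about 6 to 18 points over the same range of *b*. The 64% ratio does not depend on the number.
- *True step at the median:* the direction reverses. A 2.4-episode step gives 18.0% for the full score against 26.8% for the split; a 4.8-episode step gives 56.0% against 75.4%.

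**The case against.** The strongest reply is that D.10.5 never says scores will be dichotomized. It offers examples in exploratory language and refers to multivariate analysis. That stands as a limit: cutting is inferred from the words high and subgroup and from a gate placed on the interaction with the subgroup. It is the natural reading but not a stated commitment. If a continuous term was intended, the text needs the same clarification.

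A reader might infer that the plan forfeits 8 to 19 points of power. The documents do not support that as a property of the plan. The range needs a median split, a normal modifier, linearity and 1.2 to 2.4 episodes per SD. Other settings in the table give losses of about 2 to 26 points, and a step at the cut gives a gain. The upper value is also strong: with an average effect of 2.4 episodes, modification of 2.4 per SD means no benefit one SD below the mean and 4.8 episodes one SD above it.

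A reader might also blame the p<0.05 gate. Both tests compared here use the same level, so the gate does not create the loss. Requiring an interaction before reading subgroup estimates guards against false subgroup claims.

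Finally, a reader might infer that the mechanistic aims are compromised. They are not: Aims 2 and 3 concern mediation, tested by structural equation modeling of changes in autonomic parameters and anxiety. Effect modification is not an aim.

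**Conclusion.** The point holds as a minor, conditional improvement. What is firm is that D.10.5 describes its subgroups as defined in advance but gives neither measure nor cut for high anxiety or autonomic imbalance, and plans no continuous-score interaction.

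The power cost depends on assumptions. With linear modification and a normal modifier, a median split keeps 64% of the information. For anxiety with 136 completers, that is a loss of about 8 points at 1.2 episodes per SD (27.2 − 19.0) and 19 points at 2.4 (77.2 − 57.9). The documents posit no threshold, and the split gains only if its cut falls at or near a real one, so the continuous term is the better default. The analysis remains exploratory: at 1.2 per SD even the full score has only about 27% power, so a null result says little under either method.

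**What to change.** Amend D.10.5 as follows.
- Name a limited set of modifiers, for example one anxiety score, plus high-frequency heart rate variability (transformed if skewed) and pre-ejection period at the site that measures them.
- Test treatment by continuous score in the ANCOVA, with the score's main effect and a check for nonlinearity, such as a treatment-by-squared-score term.
- Apply the existing p<0.05 gate to the continuous interaction. If it is met, report the estimated treatment effect at chosen percentiles of the score, for example the 25th, 50th and 75th.
- Label the results exploratory and state the number of interaction tests. Three independent tests at 0.05 carry a 1 − 0.95³ = 14% chance of at least one false positive; four carry 1 − 0.95⁴ = 19%.
- Keep categorical subgroups for past treatment and psychoactive medication use.

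The cost is a few sentences and no new data. The downside is that linearity is assumed: a true threshold effect would be detected less well, and the nonlinearity check has little power at this sample size.

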Appendix A: Summary of Measures & Procedures at Study Visits

Measures	Telephone Screening	Screening Clinic Visit	Run-in period*	Baseline Clinic Visit	1week Clinic Visit	3-week Phone Call	6-Week Clinic Visit	9-week Phone Call	12-week Final Visit	24-week Mail-in
Brief telephone screening interview	X									
Informed consent and HIPAA documentation		X								
Demographic, medical & surgical history		X								
Review of current and past medications		X							X	
Alcohol and tobacco use questionnaires		X								
Height and weight measurement		X							X	
Heart rate and blood pressure measurement		X		X	X		X		X	
RESPeRATE control device run-in			X							
Review of 3-day voiding diary				X			X		X	X
Overactive Bladder Questionnaire				X			X		X	X
Urgency Severity & Impact Scale				X			X		X	X
Urogenital Distress Inventory				X			X		X	X
Spielberg State-Trait Anxiety Inventory				X			X		X	X
Hospital Anxiety and Depression Scale				X			X		X	X
Perceived Stress Scale				X			X		X	X
Center for Epidemiologic Studies Depression				X			X		X	X
Randomize to active versus control device				X						
Self-management OAB pamphlet distributed				X						
Heart rate variability measurements				X					X	
Impedance cardiography measurements				X					X	
3-day wrist actigraphy				X					X	
Sleep diary (to accompany actigraphy)				X					X	
Adverse events assessment				X	X	X	X	X	X	
Downloading of RESPeRATE device data				X	X		X		X	
Satisfaction questionnaire									X	

REFERENCES CITED

